### 9.8.4 Overall Survival (OS)

The OS (in months) is defined as the time from first treatment to death. Patients who did not die during the study will be censored at the last known alive date.

$$OS = [(Date of death - Date of first study treatment) + 1] / 30.4375$$

For censored patients:

$$OS = [(Last known alive date - Date of first study treatment) + 1] / 30.4375$$

The last known alive date will be determined among study treatment administrations, any visits where at least one assessment has been completed, or any follow-up assessment where the patient has been confirmed to be alive.

OS will be analyzed using the same Kaplan-Meier method used to analyze the DOR.

Part B, OS will be compared between ulixertinib and physician's choice of treatment using a Log Rank Test or other appropriate test if the proportional hazards assumption does not hold.

## 9.9 SAFETY DATA ENDPOINTS AND ANALYSES

All safety analyses will be performed on the Safety Analysis Set using descriptive statistics.

All safety data will be presented by group and overall, for both Part A and Part B, unless otherwise specified in the specific section.

### 9.9.1 Adverse Events (AEs)

The following definitions will be used:

- **Treatment-emergent AEs (TEAEs):** Treatment-emergent adverse event (TEAE) is defined as any AE that emerges during on-treatment period, after the 1st dose of the study agent.
- **Related AEs:** AEs suspected by the Investigator and/or Sponsor to have a relationship to study treatment (as recorded on the AE eCRF page, Causality = Related, Possibly Related, or missing).
- **Serious Adverse Events (SAE):** serious AEs (as recorded on the AE eCRF page, Does AE Meet the Definition of an SAE = Yes).
- **AEs leading to treatment discontinuation:** AEs leading to permanent discontinuation of study treatment (as recorded on the AE eCRF page, Action taken with study treatment = Drug withdrawn).
- **AEs leading to dose reduction:** AEs leading to dose reduction of study treatment (as recorded on the AE eCRF page, Action taken with study treatment = Dose Reduced).
- **AEs leading to treatment interruption:** AEs leading to treatment interruption of study treatment (as recorded on the AE eCRF page, Action taken with study treatment = Drug Interrupted).
- **AEs leading to Death:** adverse event leading to death (as recorded on the AE eCRF page, Results in death, or Outcome = Fatal, or Grade = 5).

An overview summary table will present the number and percentage of patients with a TEAE, including:

- TEAEs / TEAEs related to study treatment

- SAEs / SAEs related to study treatment
- TEAEs leading to treatment discontinuation / TEAEs related to study treatment leading to treatment discontinuation
- TEAEs leading to treatment discontinuation within 1 cycle / TEAEs related to study treatment leading to treatment discontinuation within 1 cycle
- TEAEs leading to treatment discontinuation following 1 cycle / TEAEs related to study treatment leading to treatment discontinuation following 1 cycle
- TEAEs leading to treatment interruption / TEAEs related to study treatment leading to treatment interruption
- TEAEs leading to treatment interruption within 1 cycle / TEAEs related to study treatment leading to treatment interruption within 1 cycle
- TEAEs leading to treatment interruption following 1 cycle / TEAEs related to study treatment leading to treatment interruption following 1 cycle
- TEAEs leading to dose reduction / TEAEs related to study treatment leading to dose reduction
- TEAEs leading to dose reduction within 1 cycle / TEAEs related to study treatment leading to dose reduction within cycle 1
- TEAEs leading to dose reduction following 1 cycle / TEAEs related to study treatment leading to dose reduction following cycle 1
- TEAEs leading to death / TEAEs related to study treatment leading to death
- TEAEs with grade  $\geq 3$  / TEAEs related to study treatment with grade  $\geq 3$

In addition, the following tables will be produced by SOC and PT:

- TEAEs / TEAEs related to study treatment
- Serious TEAEs / Serious TEAEs related to study treatment
- TEAEs and maximum CTCAE grade / TEAEs related to study treatment and maximum CTCAE grade
- TEAEs leading to treatment within/following discontinuation / TEAEs related to study treatment leading to treatment discontinuation
- TEAEs leading to treatment within/following interruption / TEAEs related to study treatment leading to treatment interruption
- TEAEs leading to dose reduction within/following cycle 1 / TEAEs related to study treatment leading to dose reduction within/following cycle 1
- TEAEs leading to death / TEAEs related to study treatment leading to death

The following tables will be produced by PT:

- TEAEs / TEAEs related to study treatment
- Serious TEAEs / Serious TEAEs related to study treatment

A patient with multiple occurrences of an AE will be counted only once in the AE category. SOCs will be sorted by descending order of frequency for the overall group, PTs will be sorted by descending order of frequency for the overall group within each SOC.

All deaths will be summarized and listed with the corresponding reasons, split by overall deaths, and deaths occurring after the first dose of ulixertinib.

The following listings will be provided:

- All AEs
- TEAEs
- SAEs
- Deaths

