10.4.4 Time Period and Frequency for Event Assessment and Follow-up

The occurrence of an AE or SAE may come to the attention of study personnel during study visits and interviews of a study patient presenting for medical care, or upon review by a study monitor. At each study visit, the investigator or their designee will inquire about the occurrence of AE/SAEs since the last visit.

Any medical condition that is present at the time that the patient is screened will be considered as baseline and not reported as an AE. However, if the study patient's condition deteriorates at any time during the study, it will be recorded as an AE.

Changes in the severity of an AE will be documented to allow an assessment of the duration of the event at each level of severity to be performed. AEs characterized as intermittent require documentation of onset and duration of each episode.

All reportable events will be recorded with start dates occurring any time after informed consent is obtained through and including 30 calendar days after the last administration of ulixertinib. Any SAE occurring after the reporting period must be promptly reported if a causal relationship to the study product is suspected. If the patient begins a new anti-cancer therapy, the safety reporting period ends at the time the new treatment is started, however, death must always be reported when it occurs during the 30-day reporting period irrespective of intervening treatment.

All events will be followed for outcome information in accordance with good medical practice until they are resolved, stabilize, or judged no longer clinically significant or, if a chronic condition, until fully characterized. Any AEs that are considered drug-related (possibly related, related) must be followed until resolution or until stabilization.

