11.5.7.1 Adverse Events (AE)

AEs will be coded using the Medical Dictionary for Regulatory Activities (MedDRA). System Organ Class, High-Level Group Term, High Level Term, Preferred Term, and Lower-Level Term will be attached to the clinical database.

AEs will be summarized based on the date of onset for the event. Summaries (number and percentage of patients) of treatment-emergent AEs will be provided by System Organ Class and Preferred Term, by group/tumor histology and overall.

Treatment-emergent adverse event (TEAE) is defined as any AE that emerges during treatment having been absent pre-treatment or worsens relative to the pre-treatment state.

Events that are considered study drug-related, deaths, SAEs, and AEs resulting in study drug discontinuation will also be tabulated by System Organ Class and Preferred Term.

A tabulation will also be provided that summarizes treatment-emergent AEs by maximum severity (i.e., CTCAE grade).

All AEs, including treatment-emergent and non-treatment-emergent AEs, will be listed in patient data listings.

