**Table 2. Analysis periods**

Phase	Period	Definition
Part A and Part B	PRE-TREATMENT	From informed consent form (ICF) signature to the day before first dose of study treatment.
	ON-TREATMENT	From the day of first dose of study treatment to ≤14 ± 3 days after last dose of study treatment (date of EOT visit), or the earliest date of subsequent anti-cancer drug therapy – 1 day, whichever occurs first.
	FOLLOW-UP	From day ≤14 ± 3 after last dose of study treatment, or the earliest date of subsequent anti-cancer drug therapy, whichever occurs first, to end of study. End of study is date of completion / discontinuation from the study as collected in the CRF or the last recorded assessment in the database if the patient has not completed/discontinued the study at the time of the analysis.

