## 11 Changes to Planned Analyses

No major changes to analyses planned in the protocol are expected.

A new analysis population was defined to further investigate efficacy. Although the SAP will be signed and finalized prior to the first study analysis, this new analysis population is for exploratory purposes only.

Demographic and baseline data was planned in the Protocol to be reported for all analysis populations. However, at least for Part A, this will only be reported on FAS. For Part B, this may

be revised and additional tables may be added for each analysis set.

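### SAP 9.9.1 drops the worsening limb of the protocol's TEAE definition without declaring it, so an AE that starts between consent and first dose, worsens on ulixertinib and stays one record is not a TEAE

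*SAP*

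**What the plan says.** Protocol 11.5.7.1 defines a TEAE as "any AE that emerges during treatment having been absent pre-treatment or worsens relative to the pre-treatment state". The definition has two limbs: new on treatment, or worse than before treatment.

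SAP 9.9.1 keeps one limb. A TEAE there "is defined as any AE that emerges during on-treatment period, after the" first dose of the study agent. SAP Table 2 starts the on-treatment period at the first dose ("From the day of first dose of study treatment to").

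Protocol 10.4.4 sets the recording rules:

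- On the start of collection: "All reportable events will be recorded with start dates occurring any time after informed consent is obtained". The Schedule of Activities puts screening at Day -28 to -1, so start dates before dosing are possible.
- On conditions found at screening: "Any medical condition that is present at the time that the patient is screened will be considered as baseline and not reported as an AE". If such a condition later deteriorates, that is recorded as an AE.
- On changes of grade: "Changes in the severity of an AE will be documented to allow an assessment of the duration of the event at each level of severity".

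SAP section 11 states that "No major changes to analyses planned in the protocol are expected". It mentions the new analysis population and the narrower reporting of demographic and baseline data, but not the TEAE definition.

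**The concern.** The protocol decides treatment emergence by comparison with the patient's state before treatment. The SAP decides it by when the event emerged. The two differ for an AE that begins in screening and gets worse on drug: an event that is Grade 1 before the first dose and Grade 3 afterwards, held as one record, qualifies under the protocol and not under the SAP.

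This matters because SAP 7.2 says the final report will be an abbreviated CSR focusing on safety, and the incidence and severity of AEs are a secondary endpoint. The TEAE flag feeds the tables of incidence, relatedness, maximum grade, discontinuation, interruption, dose reduction and death.

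**Working it through.** No power, alpha or event count is involved. The check sets the two definitions side by side and follows each kind of event through them.

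**Classification**

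1. New AE after first dose: a TEAE under both definitions.
2. Condition present at screening that deteriorates on ulixertinib: a TEAE under the protocol. Section 10.4.4 makes the deterioration an AE, so it is also a TEAE under the SAP if it is dated at the deterioration and falls in the on-treatment period.
3. AE starting after consent and before first dose, worsening on ulixertinib, kept as one record: a TEAE under the protocol, **not** under the SAP.
4. As case 3, but the worsening is entered as a new record with its own start date: a TEAE under both.
5. Pre-dose AE with the start day missing, in the month of first dose: SAP 7.6 sets the start to the first-dose date, so it is a TEAE under the SAP.
6. Pre-dose AE that improves after dosing, with the improvement entered as a new record (for example Grade 2 to Grade 1): neither absent before nor worse, so not a TEAE under the protocol. Under an onset-only rule it is counted as one.

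Only case 3 is lost. Case 6 is the opposite error, and arises only if each grade change opens a new record. A comparison with the pre-dose grade handles both.

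**Tables in scope**

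From the SAP's list of outputs, the TEAE tables marked for the final analysis are 14.3-1.1 to 14.3-1.5 (5 tables) and 14.3-1.10 to 14.3-1.31 (31 - 10 + 1 = 22 tables): 5 + 22 = 27.

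Two places are not clearly limited to TEAEs. Table 14.3-1.1 has rows for any SAE and any related SAE, and the programming note for Table 14.3-1.5 selects SAEs by causality. A serious event of the case 3 type might still appear there.

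**Other outputs for a case 3 event**

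- Listing 16.2.7-1 (all AEs) shows term, dates, a TEAE flag and an SAE flag. Its shell has no column for grade, causality or action taken.
- Those columns are in Listing 16.2.7-2, which is restricted to TEAEs. Listing 16.2.7-3 repeats that layout for serious AEs.
- The shift tables from baseline to worst value cover laboratory tests and vital signs, not symptoms.
- Table 14.1-4.2 counts dose changes and interruptions by reason, including adverse event, with no TEAE filter. Table 14.3-1.24 counts TEAEs leading to dose reduction. One report could therefore show an AE-driven reduction in the first table and omit the event from the second.

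So a non-serious, non-laboratory case 3 event would have its on-treatment grade in no AE table or listing.

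**The case against.** The strongest reply is that the gap is narrow and depends on a recording practice the documents do not state. The shell of Listing 16.2.7-2 has one start date, one end date and one grade per AE. That layout fits a new record at each grade change, in which case on-treatment worsening has its own start date and already counts. Protocol 10.4.1, which includes exacerbation of pre-existing conditions or events among AEs, leans the same way. Protocol 11.5.7.1 also says "AEs will be summarized based on the date of onset for the event", which could be read as supporting an onset rule. Pre-dose AEs may be few: the Schedule of Activities first marks AE assessment at Visit 2, and the screening procedures list none. Safety analysis is descriptive, and all AEs are listed.

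Much of this stands as a limit on scope. It does not remove the mismatch. Neither a listing shell nor section 10.4.1 settles how the eCRF stores a grade change, and the wording of 10.4.4 on duration at each severity level fits one event with several grades equally well. The onset sentence cannot cancel the worsening limb of the definition in the same section without emptying it. The listing of all AEs does not carry the grade.

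A reader might infer that every event starting before first dose and worsening on drug vanishes from every TEAE table. The documents do not support that, given cases 2, 4 and 5 and the SAE rows. A reader might also infer that worsening of cancer symptoms such as fatigue or nausea is the signal mainly lost. Where those symptoms are already present at screening, their deterioration is recorded as an AE and can count.

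**Conclusion.** The SAP narrows the protocol's TEAE definition and does not say so. The effect is confined to AEs with onset between informed consent and first dose that worsen on ulixertinib and stay one record. Those events leave the tables restricted to TEAEs, within a set of 27 marked for the final analysis.

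The number of such events cannot be estimated. The documents give no rate of AEs in screening and no rate of worsening among them. The enrolment figures of 38 per group and 228 in Part A are planned targets for a study that SAP 7.2 says was terminated early, so they are not usable denominators.

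The conclusion rests on reading the SAP sentence as written, with emergence judged from onset. If sites open a new record at each worsening, nothing is lost, but records opened on improvement would then be counted wrongly. Either way the definition should be corrected before the safety tables are final.

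**What to change.** Restore the protocol's worsening clause in SAP 9.9.1. One workable form keeps AEs that are new on or after first dose and adds any AE with pre-dose onset whose CTCAE grade after first dose, within the TEAE window, exceeds its highest pre-dose grade. The post-dose grade is then used for maximum severity. The protocol says only that the event worsens; the grade comparison is a proposed way to apply it.

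Also state how worsening is recorded and dated, as a new record or as a severity change within a record, so that the flag can be derived and a record opened on improvement is not counted as emergent. If the sponsor prefers the narrower definition, declare and justify it in SAP section 11.

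The cost is one extra derivation and slightly changed TEAE counts: up for restored worsening, down for any improvement records removed. It depends on the pre-dose grade being available in the collected severity data. Section 10.4.4 requires severity changes to be documented, but if each record holds a single grade, the pre-dose grade must come from elsewhere. That should be checked first.

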10.4.2 Definition of Serious Adverse Events (SAE)

A Serious Adverse Event (SAE) is any untoward medical occurrence that occurs at any dose (including after the ICF is signed and prior to dosing) that:

- Results in death
- Is life-threatening (patient is at immediate risk of death from the event as it occurred)
- Requires in-patient hospitalization (formal admission to a hospital for medical reasons) or prolongation of existing hospitalization
- Results in persistent or significant disability/incapacity
- Results in a congenital anomaly/birth defect

Important medical events that may not result in death, are not life-threatening, or do not require hospitalization may be considered SAEs when, based on appropriate medical judgment, they may jeopardize the patient and may require medical or surgical intervention to prevent one of the outcomes listed in this definition. Examples of such events include allergic bronchospasm requiring intensive treatment in an emergency room or at home, blood dyscrasias or convulsions that do not result in in-patient hospitalization, or the development of drug dependency or drug abuse.

Hospitalizations for elective surgery or other medical procedures that are not related to a treatment-emergent AE are not considered SAEs.

Progression of the malignancy under study (including signs and symptoms of progression) should not be reported as an SAE unless the outcome is fatal during the study or within the safety reporting period (see below). If the malignancy has a fatal outcome during the study or within the safety reporting period, then the event should be reported using the term “disease progression” with a CTCAE severity of Grade 5.

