**PROGRAMMING NOTES:**

- Repeat Table 14.3-1.2
- Present Serious TEAE: TEAEs with SAE =” Yes”.
- Add footnote:  
“Serious TEAE: TEAEs with SAE =” Yes”.”

Table 14.3-1.5 – Summary of Related Serious Treatment-emergent Adverse Events by System Organ Class and Preferred Term Safety Analysis Set

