**PROGRAMMING NOTES:**

- Repeat Table 14.3-1.2
- Present Related Serious TEAE: SAEs with causality=Related, Possibly Related or missing.
- Add footnote:  
“SAEs with causality=Related, Possibly Related or missing.”

**Sponsor:** BioMed Valley Discoveries

**Protocol:** BVD-523-ABC

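### The SAP and shells contradict themselves on whether the serious-event summaries are limited to treatment-emergent events, so SAEs outside the on-treatment period may enter some tables and not others

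*SAP*

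**What the plan says.** **Definitions (SAP 9.9.1).** A TEAE "is defined as any AE that emerges during on-treatment period", after the first dose. SAEs are "serious AEs (as recorded on the AE eCRF page, Does AE Meet the Definition of an SAE = Yes", with no reference to timing. Related events are those with "Causality = Related, Possibly Related, or missing", again with no reference to timing.

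**Overview (SAP 9.9.1 and shell Table 14.3-1.1).** The lead-in is "An overview summary table will present the number and percentage of patients with a TEAE, including", and the table title also calls it a summary of treatment-emergent events. Of the row pairs that follow, only "SAEs / SAEs related to study treatment" is not worded in terms of TEAEs. The shell carries this over as 'Any SAE' and 'Any Related SAE', with no programming note.

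**Serious-event tables.** The SAP text asks for serious TEAEs, all and related, by SOC/PT and by PT. The notes for the all-serious Tables 14.3-1.4 and 14.3-1.8 begin "Present Serious TEAE: TEAEs with SAE" and require that flag to be Yes. The notes for the related Tables 14.3-1.5 and 14.3-1.9 say "Present Related Serious TEAE: SAEs with causality=Related, Possibly Related or missing", and the same selection is to be printed as a footnote.

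**What is collected.** Protocol 10.4.2 counts an SAE "at any dose (including after the ICF is signed and prior to dosing". Protocol 10.4.4 records events from consent to 30 days after the last dose. The on-treatment period in SAP 7.3, Table 2, is shorter. It starts on the day of the first dose and ends at the end-of-treatment visit (≤14 ± 3 days after the last dose) or the day before new anti-cancer drug therapy, whichever comes first.

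**Use.** The safety analysis set holds dosed patients only (SAP 8). Tables 14.3-1.1, 14.3-1.4 and 14.3-1.5 are flagged for the final analysis; 14.3-1.8 and 14.3-1.9 are not.

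**The concern.** The related-serious table ought to be a subset of the all-serious table, and the overview counts ought to agree with both. The selection rules as written guarantee neither. SAP 7.2 says that the abbreviated report will focus on safety, so the SAE and related-SAE lines are among the figures that readers will look at first. Two programmers working from the same documents could produce different counts. One of them would print, under a treatment-emergent title, a footnote that describes a different set of events.

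The two ends of the window raise different problems. An SAE before the first dose cannot be an effect of the drug, but it would be classed as related if its causality field were blank. An SAE after the on-treatment period may well be drug-related, so it should not drop out of sight either.

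**Working it through.** No published figure needs reproducing. The check traces two events through the rules. Both occur in patients who receive at least one dose, so both patients are in the safety analysis set.

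- **Event A:** SAE after consent and before the first dose, causality blank.
- **Event B:** SAE with onset after the end-of-treatment visit and within 30 days of the last dose, causality Possibly Related, no new anti-cancer therapy.

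**Can event B exist?** The latest end-of-treatment visit within its window is 14 + 3 = 17 days after the last dose. Events are recorded to day 30. That leaves at least 30 − 17 = 13 days (days 18 to 30) in which an SAE is recorded but is not a TEAE. With the visit on day 14 the gap is 30 − 14 = 16 days. If new anti-cancer therapy starts, the reporting period closes too, except that deaths within the 30 days must still be reported (Protocol 10.4.4). Under Protocol 10.4.2, fatal progression within the safety reporting period is also reported, as a Grade 5 event.

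**Where do A and B land?**

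| Output | Literal definition or note | Title, lead-in or SAP text |
|---|---|---|
| 14.3-1.1, any SAE | A and B counted | neither |
| 14.3-1.1, any related SAE | A and B counted | neither |
| 14.3-1.4, all serious | neither | neither |
| 14.3-1.5, related serious | A and B counted | neither |

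The columns disagree in three of the four rows. In the literal column, A and B are in the related-serious table and missing from the all-serious table. By the same wording, 14.3-1.9 stands to 14.3-1.8 as 14.3-1.5 does to 14.3-1.4.

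**Size.** Let N be the dosed patients, S those with a serious TEAE, and K those whose only SAEs fall outside the on-treatment period. The literal overview count is S + K, against S in Table 14.3-1.4, so the difference is K/N. The documents give no value for K. One patient is worth 1/38 = 2.6 points in a group of planned size and 1/228 = 0.4 points overall. If fewer patients were dosed because of the early termination, each would weigh more.

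For the related table, let R be the patients with a related serious TEAE. Let K_R be those without one who have an SAE outside the window that is classed as related. The literal count is R + K_R, which exceeds S only if K_R > S − R. With assumed values S = 30 and K_R = 2, this needs R ≥ 29, so that nearly every serious TEAE patient has a related event. At preferred-term level a single event is enough for the two tables to conflict.

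**The case against.** The strongest reply is that the intent is clear and the rest is loose wording. The overview lead-in and title both speak of TEAEs. Table 14.3-1.5 has a treatment-emergent title, repeats the layout of the TEAE table, is labelled related serious TEAE in its own note, and is described that way in the SAP text. Only the selection after the colon and the footnote depart from this. That stands, and it rules out two stronger readings that a reader might infer: that the plan has decided to count pre-dose SAEs, and that the related-serious table is simply unrestricted. It does not remove the defect, because the selection rule and footnote are what a programmer implements and a reader sees.

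Other points also limit the concern:

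- Blank causality should be rare. Protocol 10.4.6 asks for the investigator's assessment in the initial SAE report and has the CRO safety team chase missing information.
- Screen failures do not enter these tables. The screening biopsy can be waived or met with archival tissue, so it does not imply a pre-dose SAE rate.
- The schedules of activities start adverse-event recording at Visit 2, in tension with recording from consent, so few pre-dose events may be captured.
- Listing 16.2.7-1 covers all patients, has separate TEAE and SAE columns, and is in the final analysis. Events outside the window are therefore not hidden, although its shell shows no causality column.
- The safety analyses are descriptive, with no test or decision attached.

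It could also be argued that all SAEs were meant, since Protocol 11.5.7.1 mentions tabulating SAEs without a treatment-emergent qualifier. In that case Tables 14.3-1.4 and 14.3-1.8 would be the ones to change. Either way, one rule is needed.

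**Conclusion.** The concern holds as an internal contradiction. The SAP text and titles limit the serious-event summaries to treatment-emergent events; the SAE definition behind the overview rows, and the notes and footnotes of Tables 14.3-1.5 and 14.3-1.9, do not. On the literal wording, an SAE outside the on-treatment period, at either end, could appear in the overview and in the related-serious table while missing from the all-serious table.

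This rests on three conditions: the patient was dosed, such an SAE was recorded, and, for the related counts, its causality is Related, Possibly Related or blank. The documents give no frequency for any of these. A reader might infer that the headline SAE rates are inflated by a known number of points, or that the related total will exceed the all-serious total. The first would need assumed rates; the second would need nearly all serious TEAE patients to have a related event. Neither is supported.

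The point is worth correcting before the final tables are run, because three of the affected tables are in a safety-focused report and the correction is cheap.

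**What to change.** 1. In SAP 9.9.1 and shell Table 14.3-1.1, relabel the two rows 'Any serious TEAE' and 'Any related serious TEAE'.
2. In the notes and footnotes of Tables 14.3-1.5 and 14.3-1.9, select TEAEs with the SAE flag equal to Yes and a causality entry of Related, Possibly Related or missing. As the list of outputs stands, the 14.3-1.9 edit affects no final output, but it keeps the shells consistent.
3. Add separate overview rows for SAEs before the first dose and for SAEs after the on-treatment period, each for all and for related events. A pre-dose row alone would leave late, possibly drug-related SAEs in no summary row.
4. State that Listing 16.2.7-3 contains all SAEs, with a treatment-emergent flag. Its shell now repeats the TEAE listing restricted to serious events, so it may omit those outside the window.

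The cost is a few lines of SAP text, a few extra table rows, edits to two notes with their footnotes, and one listing column. No new data are needed.
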